9.2 Study or Site Termination

If the Sponsor, Investigator, Independent Safety Monitor, Study Monitor, or appropriate regulatory officials discover conditions arising during the study that indicate that the study should be halted or that the study center should be terminated, this action may be taken after appropriate consultation among the Sponsor, Investigator, Independent Safety Monitor, and Study Monitor.

Conditions that may warrant termination of the study include, but are not limited to, the following:

- The discovery of an unexpected, serious, or unacceptable risk to the subjects enrolled in the study
- A decision on the part of the Sponsor to suspend or discontinue testing, evaluation, or development of the product
- A study conducted at a single study site or a single study site in a multicenter study may also warrant termination under the following conditions:
 - Failure of the Investigator to enroll subjects into the study at an acceptable rate
 - Failure of the Investigator to comply with pertinent regulations of appropriate regulatory authorities
 - Submission of knowingly false information from the research facility to the Sponsor, Study Monitor, or appropriate regulatory authority
 - Insufficient adherence to protocol requirements

Study termination and follow-up will be performed in compliance with the conditions set forth in the International Conference on Harmonization (ICH) sixth efficacy publication (E6) on Good Clinical Practice, section 4.12, ICH E6 4.13, ICH E6 5.20, and ICH E6 5.21.

10 ADVERSE EVENTS

Adverse events will be captured in the CRF for this study.

10.1 Definitions

10.1.1 Adverse Event Definitions

Adverse events are defined according to ICH Harmonized Tripartite Guideline E2A and 21 CFR 312.32.

Adverse event (AE) – is any untoward medical occurrence in a subject or clinical trial subject administered a trial product and which does not necessarily have a causal relationship with this treatment.

An adverse event can therefore be any unfavorable and unintended sign (including an abnormal laboratory finding, for example), symptom, or disease temporally associated with the use of a medicinal product, whether or not considered related to the medicinal product.

The following is not considered or documented as an AE in study records:

- Pre-planned procedure (documented as concomitant illness on the CRF at screening) unless the condition for which the procedure was planned has worsened from the first trial-related activity after the subject has signed the informed consent form.
- Pre-existing conditions found as a result of screening procedures unless the condition worsens during treatment.
- Events which are pre-defined as part of the efficacy analysis. However, if events are serious as defined below, events must be reported as such.

Serious adverse event (SAE) – is any untoward medical occurrence or effect that at any dose: results in death; is life-threatening (this refers to an event in which the subject was at risk of death at the time of the event; it does not refer to an event that hypothetically might have caused death if it was more severe); requires in-subject hospitalization or prolongation of existing hospitalization; results in persistent or significant disability or incapacity; is a congenital anomaly or birth defect; is judged medically important (this refers to an event that may not be immediately life-threatening or result in death or hospitalization, but may jeopardize the subject or may require intervention to prevent one of the other outcomes listed).

10.1.2 Adverse Event Assessment Definitions

Severity

The maximum severity of an adverse event is assessed by the investigator using the following definitions:

- Mild: Transient symptoms, no interference with the subject's daily activities.
- Moderate: Marked symptoms, moderate interference with the subject's daily activities.
- Severe: Considerable interference with the subject's daily activities, unacceptable.

Relationship

The causal relationship between an adverse event and the trial product is assessed by the investigator using the following definitions:

- Probable: Good reasons and sufficient documentation to assume a causal relationship.
- Possible: A causal relationship is conceivable and cannot be dismissed

- **Unlikely:** The event is most likely related to an etiology other than the trial product.

An adverse event is considered causally related to the use of the trial product when the relationship assessment is probable or possible. Events assessed as unlikely related to the use of trial product will generally be considered as having no relationship to treatment.

Outcome

The outcome of an adverse event is assessed by the investigator using the following definitions:

- **Recovered:** Fully recovered, or by medical or surgical treatment the condition has returned to the level observed at the first trial-related activity.
- **Recovering:** The condition is improving and the subject is expected to recover from the event. This term should only be used when the subject has completed the trial.
- **Recovered with sequelae:** As a result of the AE the subject suffered persistent and significant disability/incapacity (e.g. became blind, deaf, paralyzed). Any AE recovered with sequelae should be classified as SAE.
- **Not recovered:** The subject's condition has not improved and the symptoms are unchanged
- **Fatal**
- **Unknown:** The subject's condition is unknown. This term should only be used when no other definition is possible (e.g. the subject is lost to follow-up).

10.2 Collection, Recording and Reporting of Adverse Events

For this study, all events meeting the definition of an adverse event must be collected and reported from the first trial-related activity after the subject signs the informed consent and until end of post-treatment period.

The investigator should record the diagnosis, if available. If no diagnosis is available the investigator should record each sign and symptom as individual adverse events.

The investigator must report initial information on all serious adverse events within 24 hours of obtaining knowledge of the event. Furthermore, the investigator must complete the SAE forms within five days of obtaining knowledge of the SAE. The monitor must be informed accordingly.

The investigator must inform the IRB in accordance with local requirements in force and the ICH guidelines for GCP and the Food and Drug Administration (FDA) Title 21 Code of Federal Regulations, Part 312.32.

10.3 Follow-up of Adverse Events

All adverse events classified as non-serious adverse events that are both classified as severe and possibly or probably related to the investigational medicinal product must be followed until the subject has recovered and all queries have been resolved.

For cases of chronic conditions, follow-up until “recovered” is not required. After the subject has completed the trial, these cases can be closed with the outcome “recovering” or “not recovered”.

All other non-serious adverse events must be followed until the outcome of the event is “recovering” (for chronic conditions), “recovered” or until the last subject contact/visit/end of post-treatment follow-up period, whichever comes first, and until all queries related to the adverse event have been resolved.

Follow-up of Serious Adverse Events

All adverse events classified as serious should be followed until the outcome of the event is “recovered”, “recovered with sequelae”, or “death” and until all queries have been resolved. For cases of chronic conditions and cancer, follow-up until “recovered”, “recovered with sequelae” or “death” is not required. After the subject has completed the trial, these cases can be closed with the outcome “recovering” or “not recovered”.

11 STATISTICAL METHODS AND DATA ANALYSIS

The following text provides a general description of the statistical methodology for the assessment of safety and tolerability of oral ifetroban in this randomized, double-blind, placebo-controlled, multiple dose study in subjects with DMD. Details of the statistical analyses will be provided in the Statistical Analysis Plan, which will be finalized prior to database lock. All recorded data will be listed.

11.1 Sample Size Determination

The sample size is based on the comparison of each dose level of ifetroban (Low Dose or High Dose) to placebo with respect to change from baseline in LVEF using CMR for each disease stage, early (LVEF > 45%) or advanced (current/historical LVEF 35-45%). Assuming observations from each treatment group have normal distributions with an effect size of 1.6 for the comparison of a dose of ifetroban to placebo, 8 subjects for each treatment group within disease stage will provide

power exceeding 85% for a t-test at two-sided level 0.05. Under these assumptions, 8 subjects for each treatment group within disease stage will provide power exceeding 80% for the Wilcoxon rank sum test at two-sided level 0.05. A total of 48 DMD subjects will be enrolled: 24 subjects with early stage DMD (LVEF > 45%) and 24 with advance stage DMD (current/historical LVEF 35-45%). Assuming a dropout rate of 25%, 60 subjects will be recruited to meet the target sample size of 48 subjects.

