2 SYNOPSIS

Name of Sponsor: Cumberland Pharmaceuticals	Name of Finished Product: Ifetroban Capsules	Name of Active Ingredient: ifetroban
Title of Study: A Randomized, Double-Blind, Placebo-Controlled, Multiple Dose Study with an Open-Label Extension to Determine the Safety, Pharmacokinetics and Efficacy of Oral Ifetroban in Subjects with Duchenne Muscular Dystrophy		
Study Centers (Planned): Ten Phase of Development: II		
Expected Study Duration (per subject): Screening period (12 weeks) + Treatment period (12 months) + Open-label Extension (repeatable periods of 12 months)		
Objectives: Primary Study Objective 
Assess the safety of oral ifetroban in male subjects with Duchenne Muscular Dystrophy (DMD) Secondary Study Objectives 
Evaluate the pharmacokinetics and efficacy of oral ifetroban. Exploratory Study Objectives 
Evaluate novel biomarkers for diagnosis and monitoring of cardiomyopathy in DMDEvaluate changes in daily life activity and quality of life		
Methodology: This is a randomized, double-blind, placebo-controlled, multiple dose study with an open-label extension to determine the safety, pharmacokinetics and efficacy of low or high doses of oral ifetroban compared to placebo in subjects with DMD.		
Number of subjects (planned): A total of 48 DMD subjects will be enrolled: 24 subjects with early stage DMD (LVEF > 45%) and 24 with advance stage DMD (LVEF 35% - 45% or historically documented LVEF 35%-45% and baseline LVEF less than 50%)		

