5.2 Stage of Development

CPI-IFE-007 is randomized, double-blind, placebo-controlled, multiple dose study with an open-label extension to determine the safety, pharmacokinetics and efficacy of two dose ranges of oral ifetroban in subjects with DMD.

Approximately 48 subjects will be randomly assigned to one of three treatment groups for 12 months of treatment: low-dose ifetroban, high-dose ifetroban or matching placebo, with 24 subjects within each disease stage, early (LVEF > 45%) or advance (current/historical LVEF 35%-45%). Patients who complete 12 months of treatment are eligible to participate in a repeatable open-label extension period of 12 months.

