The total duration of the study participation for each subject is up to 52 weeks. There is a repeatable optional open-label extension period where any subject completing 12 months of treatment is eligible to participate. Recruitment is planned to stop when approximately 48 subjects have completed 12 months of treatment. The end of the study is defined as the last subject's last visit/contact.

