### **3.4 Sample Size**

The sample size is based on the comparison of each dose level of ifetroban (Low-Dose or High-Dose) to placebo with respect to change from baseline in LVEF using CMR for each disease stage, early (LVEF > 45%) or advanced (LVEF 35-45%).

Assuming observations from each treatment group have normal distributions with an effect size of 1.6 for the comparison of a dose of ifetroban to placebo, 8 subjects for each treatment group within disease stage will provide power exceeding 85% for a t-test at two-sided level 0.05. Under these assumptions, 8 subjects for each treatment group within disease stage will provide power exceeding 80% for the Wilcoxon rank sum test at two-sided level 0.05.

A total of 48 DMD subjects will be enrolled: 24 subjects with early stage DMD (LVEF > 45%) and 24 with advance stage DMD (LVEF 35-45%). Assuming a dropout rate of 10%, 54 subjects will be recruited to meet the target sample size of 48 subjects.

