### **3.5 Randomization**

Subjects will be randomly assigned to one of three treatment groups: low-dose ifetroban 100 mg/day, high-dose ifetroban 300 mg/day or matching placebo, using a 1:1:1 randomization ratio. All subjects will be treated with IMP daily for a minimum of six months and a maximum of 12 months. Approximately 48 subjects shall be randomized to ensure at least 16 subjects per group will be analyzed for efficacy.

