#### **4.4.4 Multiple Comparisons/Multiplicity**

Multiplicity and multiple comparisons do not apply to these secondary and exploratory objectives. No adjustments will be made for multiple comparisons or multiplicity. Changes to Protocol Specified Analysis

There are no changes to the protocol specified analyses.

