## 8 CHANGES IN THE STATISTICAL METHODS FROM THOSE STATED IN THE PROTOCOL

Not Applicable

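### Recruiting 60 at 25% dropout gives 45 completers, not 48; the SAP plans on 10% and 54, and the documents disagree on what 48 counts

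*Protocol*

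**What the plan says.** **Protocol.** Section 11.1 and the Sample Size entry of the Synopsis size the trial at 8 subjects per treatment group within each disease stage. That is six cells and 48 subjects. Both then give the same allowance for loss: "Assuming a dropout rate of 25%, 60 subjects will be recruited to meet the target sample size of 48 subjects".

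**SAP.** Section 3.4 repeats the power statement and the target but allows for loss differently: "Assuming a dropout rate of 10%, 54 subjects will be recruited to meet the target sample size of 48 subjects". The SAP says it implements Amendment 04a. Section 4.4.4 adds "There are no changes to the protocol specified analyses", and Section 8, headed "CHANGES IN THE STATISTICAL METHODS FROM THOSE STATED IN THE PROTOCOL", is marked not applicable.

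**What 48 counts.** The usage differs by place:

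- Enrolled: "A total of 48 DMD subjects will be enrolled" (Synopsis; also Protocol 11.1 and SAP 3.4).
- Randomised: "Approximately 48 subjects will be randomly assigned to one of three treatment groups for 12 months of treatment" (Protocol 5.2).
- Randomised and also analysed: "Approximately 48 subjects shall be randomized to ensure at least 16 subjects per group will be analyzed for efficacy" (SAP 3.5).
- Completed: "Recruitment is planned to stop when approximately 48 subjects have completed 12 months of treatment" (Protocol 7.1).

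**The concern.** There are three separate problems.

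1. The Protocol's recruitment figure looks like the target multiplied by one plus the dropout rate. The correct step is to divide by one minus the rate.
2. The Protocol and SAP plan on different dropout rates and totals for the same target, and nothing says which governs.
3. The 48 cannot be both the number randomised and the number completing or analysed unless nobody drops out. SAP 3.5 puts both in one sentence.

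What could be lost is power for the within-stage LVEF comparisons on which the sample size rests. Whether anything is lost depends on when recruitment stops and on how many dropouts contribute a Month 12 value. Protocol 8.1 asks for the End of Treatment assessments after early discontinuation, which would rescue some. Protocol 11.7 and SAP 4.2 do not impute in the main analysis, whereas SAP 3.3 says early discontinuers are carried forward by LOCF. The number analysed at Month 12 therefore also depends on an unresolved contradiction about missing data.

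**Working it through.** **Inputs.** Target 48, dropout 25%, recruitment 60 (Protocol 11.1, Synopsis). Dropout 10%, recruitment 54 (SAP 3.4). Standardised effect 1.6, two-sided 0.05, 8 per cell (Protocol 11.1, SAP 3.4). Allocation 1:1:1 (Protocol 11.6).

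**Reproducing the stated recruitment figures.** The required number is N/(1 − d).

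- Protocol: 48/(1 − 0.25) = 64, so 60 is not reproduced. 48 × (1 + 0.25) = 60 gives the stated figure.
- Rate at which 60 would be right: 1 − 48/60 = 20%.
- SAP: 48/(1 − 0.10) = 53.3, rounded up to 54. This is reproduced.

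**Expected completers and the chance of reaching 48** (binomial, independent dropout):

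| Recruited | Dropout | Expected completers | P(at least 48) |
|---|---|---|---|
| 60 | 25% | 60 × 0.75 = 45 (7.5 per cell) | 23% |
| 60 | 20% | 60 × 0.80 = 48 | 58% |
| 64 | 25% | 64 × 0.75 = 48 | 57% |
| 54 | 10% | 54 × 0.90 = 48.6 | – |
| 54 | 25% | 54 × 0.75 = 40.5 | – |

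**Reproducing the stated power at 8 v 8.** For the t-test, the noncentrality is 1.6 × √(8 × 8/16) = 3.2 on 14 degrees of freedom, which gives 84.5%. The plan claims more than 85%, so it is half a point high. The exact Wilcoxon test, simulated with normal data, gives about 82%, which agrees with the claim of more than 80%.

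**Within-stage exact Wilcoxon power at effect size 1.6, by cell size:**

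| Cells | Power |
|---|---|
| 8 v 8 | 82% |
| 7 v 8 | 76% |
| 7 v 7 | 71% |
| 6 v 7 | 65% |

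**Averaged over random dropout**, with 60 recruits spread as 10 per cell and no Month 12 value from dropouts:

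- 25% dropout: 75% average power; both cells reach 8 or more in 28% of cases.
- 20% dropout: 79% average power; both cells reach 8 or more in 46% of cases.
- Difference attributable to the mismatch: about 4 points.
- For comparison, 64 recruits at 25% is 64/6 = 10.67 per cell. The average is between 77% (10 v 11) and 80% (11 v 11).

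**Pooled over stage.** 45 completers is 45/3 = 15 per arm. Exact Wilcoxon power for 15 v 15 at effect size 1.6 is about 98%.

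**The case against.** The strongest reply is that the slip has little consequence.

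- Protocol 7.1 stops recruitment on completers. If that is followed, the completer count is protected whatever figure is forecast. This stands.
- The planned Wilcoxon comparisons in Protocol 11.8.3 and SAP 6.2.1 are not split by stage. Stage appears only as an exploratory subgroup. The pooled comparison keeps about 98% power, and the primary endpoint is the incidence of adverse events. This stands too, although the within-stage comparison is the one the sample size is justified on.
- Falling below 80% is mostly not due to the arithmetic. Even 60 recruits at 20% average 79%, and 64 at 25% average between 77% and 80%, because cell sizes vary at random. This also stands: only about 4 points belong to the mismatch.
- The SAP's statements of no change concern analyses and methods, and a dropout assumption is arguably neither. That is fair, and the conflict between 25%/60 and 10%/54 does not need them.
- Recruited and enrolled are undefined. If enrolled means the target sample, several passages fit Protocol 7.1. This narrows the third problem to the two places that say 48 are randomised, both worded as approximate.

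None of this makes 25% loss from 60 leave 48. That would require the rate to mean dropouts as a share of completers (12/48), which neither document says.

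**Conclusion.** The concern holds. The recruitment figure in Protocol 11.1 and the Synopsis is wrong for its own dropout rate: it falls 3 completers short of the target, or 4 recruits short of the number needed. The SAP's 54 is correct for its own 10% but conflicts with the Protocol, and 48 has no single meaning across the two documents.

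The consequence is conditional and small. It arises only if recruitment closes at 60, dropouts supply no Month 12 CMR, and missing LVEF is not imputed. Average within-stage power is then about 75% at effect size 1.6, about 4 points lower than if dropout were 20%. That average assumes normal data, 10 recruits per cell and independent dropout at one common rate. The unsplit efficacy comparisons and the primary safety endpoint are not materially affected. It should be corrected, but it does not threaten the trial.

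**What to change.** Use one dropout rate, one recruitment figure and one definition of 48 in the Synopsis (both entries), Protocol 5.2, 7.1 and 11.1, and SAP 3.4 and 3.5. Say whether 48 counts randomised subjects or Month 12 completers, and define recruited and enrolled. Then choose one:

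- **(a)** Keep 60 and restate dropout as 20%, giving the basis for that rate, since the documents offer none.
- **(b)** Keep 25% and 60, and state 45 expected completers (7.5 per cell) with within-stage Wilcoxon power of about 75% on average at effect size 1.6. The stopping statement in Protocol 7.1 must then change, because it aims for about 48 completers.
- **(c)** Keep 25% and state 64.

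Options (a) and (b) are text edits with no extra recruitment. Option (c) raises the planned number by 4. SAP 4.3 reports the interim analysis as already done, but the documents do not give recruitment status, so whether (c) can still be acted on is unknown.

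Two side points belong in the same edit. First, reconcile the LOCF statement in SAP 3.3 with the no-imputation rules in Protocol 11.7 and SAP 4.2, because the number analysed at Month 12 depends on it. Second, change the t-test power at 8 v 8 from more than 85% to about 84% (computed 84.5%).

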11.2 Subject Populations for Analysis

11.2.1 Safety Population

All subjects who receive at least one dose of treatment will be included in the Safety Population.

Treatment emergent period for Safety Population is defined as the time from the first administration of treatment to the end of the Treatment Period.

11.2.2 Intent-to-Treat Population

The Intent-To-Treat (ITT) Population will consist of all treated subjects with at least one post-baseline assessment.

11.2.3 Per Protocol Population

The Per Protocol (PP) Population will consist of all subjects in the ITT population with no major protocol violations, including violation of inclusion or exclusion criteria or insufficient dosing where the latter includes missing more than 2 consecutive weeks of dosing for any reason or missing >20% of prescribed doses between consecutive visits.

11.3 Subgroup analysis

To assess the consistency of treatment effects across the subgroup levels, and to examine baseline biomarkers for their potential value to predict treatment response, exploratory subgroup analyses will be conducted for safety, tolerability, pharmacokinetics and efficacy with respect to age group, race, DMD disease stage, baseline LVEF, muscle strain and other CMR parameters, baseline PFT, PedsQL, GI module & NMM values and selected biomarkers prior to the study. The details will be provided in the Statistical Analysis Plan.

11.4 Interim Analysis

An early analysis will be performed when half the target enrollment has completed the six month visit and assessments. A decision to change the conduct of the study may be made based on this analysis. Key findings from the interim analysis will be summarized and distributed to limited

personnel. To maintain study integrity with respect to subsequent treatment visits, the team that will perform the early analysis and all related activities will be external and restricted from participating in data review or decisions following the early analysis but may participate in the analysis following final database lock. Statistical considerations related to the interim analysis will be provided in the Statistical Analysis Plan.

